4. STUDY DESIGN

4.1. Overall design

Figure 1 Study design overview

1MPD = 1-month post-dose.

* Blood sample only from participants in Control group.

FLU = FLU HD quadrivalent; RSV = RSVPreF3 OA investigational vaccine; BS = Blood sample from all participants (except for blood sample at Visit 3 which is only applicable for Control group).

Note: Unsolicited AEs will be collected from first dose to 30 days post-dose. SAEs and pIMDs will be collected from first dose through the entire study period. SAEs related to study participation will be collected from the time of consent.

- **Type of study:** self-contained.
- **Experimental design:** phase 3, randomized, open-label, multi-country study with 2 parallel groups (see [Figure 1](#)).
- **Duration of the study:** ~ 6 months for participants in Co-Ad group; ~ 7 months for participants in Control group.
- **Primary completion date:** Day 61 (1 month after the RSVPreF3 OA investigational vaccine dose in Control group).
- **Control:** active comparator, i.e. staggered administration of licensed FLU vaccine and RSVPreF3 OA investigational vaccine.
- **Blinding:** open-label. Refer to Section [6.3.5](#) for details.
- **Data collection:** standardized electronic Case Report Form (eCRF). Solicited events and unsolicited AEs will be collected using a participant Diary card (paper Diary card).
- **Safety monitoring:** the study will be conducted with oversight by the project Safety Review Team (SRT). Please refer to Section [10.1.5](#) for the SRT structure.
- **Vaccination schedule:**
 - **Co-Ad group:** Participants will receive a single dose of RSV investigational vaccine and a single dose of FLU vaccine at Visit 1 (Day 1).
 - **Control group:** Participants will receive a single dose of FLU vaccine at Visit 1 (Day 1), followed by a single dose of the RSV investigational vaccine at Visit 2 (Day 31).
- **Study groups:** Refer to [Figure 1](#) and [Table 6](#) for an overview of the study groups.

Table 6 Study groups and intervention

Study groups	Number of participants	Age (Min-Max)	Study interventions
Co-Ad	~514	≥65 years	RSVPreF3 OA investigational vaccine
			FLU HD
Control	~514	≥65 years	RSVPreF3 OA investigational vaccine
			FLU HD

FLU HD = FLU HD quadrivalent

4.1.1. Overview of the recruitment plan

No screening visit is planned for this study. The study is planned to be conducted at multiple sites in multiple countries. The recruitment plan will be defined by each participating site.

The recruitment plan may be adapted based on the actual number of participants enrolled in each country. In case a site would fall behind in participant recruitment, a redistribution of the enrolment target per site in the participating countries may be made. This would allow the other participating sites to enroll additional participants to ensure

full and timely enrolment of the overall targeted number of participants specified in this protocol.

The procedures for participants identification/recruitment must be approved by the Independent Ethics Committee (IEC)/Institutional Review Board (IRB) together with the material intended for participants identification/recruitment and participants use. Refer to the Study Procedures Manual (SPM) for additional details.

4.1.2. Enrolment rules

Overall, participants will be enrolled in 3 age categories reflecting an approximate age distribution in the general population with a balance between males and females. It is therefore intended to enroll:

- Approximately 25% of participants 65-69 YOA, approximately 40% of participants 70-79 YOA and approximately 10% of participants ≥ 80 YOA. The remaining approximately 25% can be distributed freely across the 3 age categories.
- Approximately 40% of participants from each sex; the remaining approximately 20% can be distributed freely between the 2 sexes.

4.1.3. Caregiver support

Study participants may decide to assign a caregiver to help them fulfilling the study procedures. Please refer to the [Glossary of terms](#) for the definition of a caregiver.

A caregiver can be appointed by the participant at any time during the study, when the participant feels it is necessary. Each caregiver should receive the caregiver information letter before providing support to the study participant. Ideally, a single caregiver should be appointed by the participant but, in some situations, it may happen that several caregivers will support a study participant throughout the conduct of the study. This should be recorded in the source documents.

Caregivers may help the study participants with performing some practical study procedures such as receiving or making phone calls to site staff, planning study visits, transcribing responses to diaries, transportation to and from the study site etc. However, at no time, the caregiver should evaluate the participant's health status while answering diaries or make decisions on behalf of the participant. At the first study visit (Visit 1) the site staff should inform the participant of the possibility to appoint a caregiver. Then at subsequent study visit(s), the site staff should check again with the participant if he/she wishes to appoint a caregiver or if there were or will be changes of caregiver.

4.2. Scientific rationale for study design

The influenza season coincides with the RSV season in temperate countries. Influenza vaccination begins at the start of the Flu season, at around the same time when the RSVPreF3 OA investigational vaccine may potentially be recommended for immunization against RSV infection. Till date, there is no data available on the safety and immunogenicity of the RSVPreF3 OA investigational vaccine when it is co-administered with an influenza vaccine.

The current study is therefore designed to assess the safety, reactogenicity and immunogenicity of the RSVPreF3 OA investigational vaccine when it is co-administered with a FLU vaccine, compared to administration of the vaccines separately. There are 2 parallel arms:

- **Co-Ad group:** Participants will receive a single dose of RSV investigational vaccine and a single dose of FLU vaccine at Visit 1 (Day 1).
- **Control group:** Participants will receive a single dose of FLU vaccine at Visit 1 (Day 1), followed by a single dose of the RSV investigational vaccine at Visit 2 (Day 31).

The study will enroll older adults ≥ 65 YOA who are primarily responsible for self-care and activities of daily living. Participants may have one or more chronic medical conditions but should be medically stable in the opinion of the investigator.

As the RSVPreF3 OA investigational vaccine is adjuvanted, all participants will be followed up for safety for 6 months post-RSV investigational vaccine administration.

The 120 μ g RSVPreF3/AS01_E vaccine formulation was selected in a previous study (RSV OA=ADJ-002), where the vaccine was administered intramuscularly according to a 0, 2-month vaccination schedule. Please refer to the IB for details.

4.3. Justification for dose

Based on the results up to 1-month post-Dose 2 from study RSV OA=ADJ-002, a single dose regimen (0.5 mL) and the 120 μ g RSVPreF3/AS01_E formulation were selected for further evaluation in the Phase 3 clinical program. The RSV OA=ADJ-002 study was designed to assess the immunogenicity of a 2-dose AS01-adjuvanted or unadjuvanted vaccine administered according to a 0-, 2-month schedule with the aim to maximize the immune response against RSV and vaccine efficacy over several seasons. Based on the data from clinical development programs for AS01-adjuvanted protein antigen vaccines in OA, such as *Shingrix* and the chronic obstructive pulmonary disease investigational vaccine, it was expected that immunological responses would reach higher levels 1 month post-Dose 2 as compared with 1 month post-Dose 1. However, the RSV OA=ADJ-002 results demonstrated that the second dose given 2 months after the first dose had no added value in terms of humoral and/or cellular immune responses. The humoral response, both in terms of RSV-A neutralizing antibody GMTs and [REDACTED] [REDACTED] peaked 1 month after the first dose, and the second dose did not increase the level observed after first dose.

The results from study RSV OA=ADJ-002 demonstrated statistically significant superiority of the 120 µg formulations in terms of RSV-A neutralizing titers over at least one of the 30 µg and 60 µg formulations with the same adjuvant content or unadjuvanted. The data demonstrated an immunologic benefit of any AS01_E or AS01_B formulations over unadjuvanted formulations in terms of frequency of RSVPreF3-specific CD4+ T cells expressing at least 2 markers. Importantly, despite lower baseline observed in OA, the AS01-containing formulations induced CD4+ T cells frequencies at a close or similar level as in Young Adults, that is not observed with the unadjuvanted formulations.

There was no safety concern detected in unadjuvanted groups to be linked to the RSVPreF3 antigen assessed for the first time in OA. The acceptable safety/reactogenicity profile in all 120 µg groups, together with the immunological benefit demonstrated for the 120 µg antigen dose, supports the selection of a 120 µg based formulation. The results also showed that all the AS01-adjuvanted formulations evaluated are considered to have a clinically acceptable safety profile. The AS01-adjuvanted formulation with the lowest reactogenicity profile, i.e., the AS01_E-based formulation, was selected. The immunological response observed after 1 vaccine dose of the AS01_E-based formulation is considered adequate for a RSVPreF3 OA candidate vaccine.

In the current study, the FLU vaccine will be administered as a single dose (recommended standard of care).

4.4. End of Study definition

A participant is considered to have completed the study if he/she returns for the last visit or is available for the last scheduled contact as described in the protocol.

End of Study (EoS): Last subject last visit (LSLV) (Contact at 6 months post-last dose).

5. STUDY POPULATION

Adherence to the inclusion and exclusion criteria specified in the protocol is essential. Deviations from these criteria are not allowed because they can jeopardize the scientific integrity, regulatory acceptability of the study or safety of the participant.

5.1. Inclusion criteria

All participants must satisfy ALL the following criteria at study entry:

- Participants, who, in the opinion of the investigator, can and will comply with the requirements of the protocol (e.g. completion of the diary cards, return for follow-up visits, ability to access and utilize a phone or other electronic communications).

Note: In case of physical incapacity that would preclude the self-completion of the diary cards, either site staff can assist the participant (for activities performed during site visits) or the participant may assign a caregiver to assist him/her with this activity (for activities performed at home). However, at no time will the site staff or caregiver evaluate the participant's health status while answering diaries or make

decisions on behalf of the participant. Refer to the [Glossary of terms](#) for the definition of caregiver.

- A male or female ≥ 65 YOA at the time of the first study intervention administration.
- Participants living in the general community or in an assisted-living facility that provides minimal assistance, such that the participant is primarily responsible for self-care and activities of daily living.
- Written or witnessed informed consent obtained from the participant prior to performance of any study-specific procedure.
- Participants who are medically stable in the opinion of the investigator at the time of first vaccination. Participants with chronic stable medical conditions with or without specific treatment, such as diabetes, hypertension, or cardiac disease, are allowed to participate in this study if considered by the investigator as medically stable.

5.2. Exclusion criteria

The following criteria should be checked at the time of study entry. The potential participant MAY NOT be included in the study if ANY exclusion criterion applies:

5.2.1. Medical conditions

- Any confirmed or suspected immunosuppressive or immunodeficient condition resulting from disease (e.g. current malignancy, human immunodeficiency virus) or immunosuppressive/cytotoxic therapy (e.g., medication used during cancer chemotherapy, organ transplantation, or to treat autoimmune disorders), based on medical history and physical examination (no laboratory testing required).
- History of any reaction or hypersensitivity likely to be exacerbated by any component of the vaccines.
- Hypersensitivity to latex.
- History of Guillain-Barré syndrome (GBS), or anaphylaxis.
- Serious or unstable chronic illness.
- Any history of dementia or any medical condition that moderately or severely impairs cognition.

Note: If deemed necessary for clinical evaluation, the investigator can use tools such as Mini-Mental State Examination (MMSE), Mini-Cog or Montreal Cognitive Assessment (MoCA) to determine cognition levels of the participant.

- Recurrent or un-controlled neurological disorders or seizures. Participants with medically-controlled active or chronic neurological diseases can be enrolled in the study as per investigator assessment, provided that their condition will allow them to comply with the requirements of the protocol (e.g. completion of diary cards, attend regular phone calls/study site visits).

- Significant underlying illness that in the opinion of the investigator would be expected to prevent completion of the study (e.g., life-threatening disease likely to limit survival up to study end).
- Any medical condition that in the judgment of the investigator would make intramuscular injection unsafe.

5.2.2. Prior/Concomitant therapy

- Use of any investigational or non-registered product (drug, vaccine, or medical device) other than the study interventions during the period beginning 30 days before the first study vaccine administration, or planned use during the study period.
- Administration of an influenza vaccine during the 6 months preceding the study FLU vaccine administration.
- Planned or actual administration of a vaccine not foreseen by the study protocol in the period starting 30 days before the first study intervention administration and ending 30 days after the last study intervention administration.

Note: In case an emergency mass vaccination for an unforeseen public health threat (e.g.: a pandemic) is recommended and/or organized by the public health authorities, outside the routine immunization program, the time period described above can be reduced if necessary for that vaccine provided it is used according to the local governmental recommendations and that the Sponsor is notified accordingly.

- Previous vaccination with an RSV vaccine.
- Administration of long-acting immune-modifying drugs or planned administration at any time during the study period (e.g. infliximab).
- Administration of immunoglobulins and/or any blood products or plasma derivatives during the period starting 90 days before the first dose of study vaccine or planned administration during the study period.
- Chronic administration (defined as more than 14 consecutive days in total) of immunosuppressants or other immune-modifying drugs during the period starting 90 days prior to the first study vaccination or planned administration during the study period. For corticosteroids, this will mean prednisone ≥ 20 mg/day, or equivalent. Inhaled and topical steroids are allowed.

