6.8. Concomitant therapy

At each study visit/contact, the investigator or his/her delegate should question the participant about all medications/products taken, and vaccinations received by the participant.

The following concomitant medication(s)/product(s)/vaccine(s) must be recorded in the eCRF:

- All concomitant medications and vaccinations, except vitamins and dietary supplements, administered during the 30-day period following each dose of study intervention.
- All concomitant medication leading to discontinuation of the study intervention or elimination from the analysis, including products/vaccines. Please refer to Sections [5.2.2](#) and [9.3.1](#) for further details.
- All concomitant medication which may explain/cause/be used to treat an SAE/pIMD including vaccines/products, as defined in Sections [8.3.1](#) and [10.3.2](#). These must also be recorded in the Expedited AE report.
- Any prophylactic medication (e.g. analgesics, antipyretics) administered on the day of study vaccination (Day 1 in the Co-Ad group, Day 1, and Day 31 in the Control group) in the absence of ANY symptom and in anticipation of a reaction to the vaccination.

The Local Medical Lead should be contacted if there are any questions regarding concomitant or prior therapy.

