3. ANALYSIS SETS

Analysis Set	Definition / Criteria
Enrolled set*	Participants who agreed to participate in a clinical study after completion of the informed consent process.
Safety/Exposed set (ES)	All participants who received a study intervention. Analysis per group is based on the study intervention administered.
Per-Protocol set (PPS)	All eligible participants who received at least one study intervention as per-protocol in the control group and all study interventions in the Co-Ad group , had immunogenicity results pre-post-dose for at least one antigen, complied with blood draw intervals (refer to intervals mentioned below) and contribution of participants to PPS at specific timepoint will be defined by timepoint, without intercurrent medical conditions that may interfere with immunogenicity and without prohibited concomitant medication/vaccination.

*All participants enrolled and included in the database will be part of the enrolled set.

Intervals for the Co-Ad group: Visit1-Visit2=30-37 days

Intervals for the Control group: Visit1-Visit2=30-37 days, Visit2-Visit3=30-37 days

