3.1.2. Elimination from Per-protocol Set (PPS)

A participant will be excluded from the populations for analysis under the following conditions:

- For codes 800, 900, 1030, 1050 and 2020: participants will be eliminated for all visits.
- For codes 1070, 1080, 1090: participants will be eliminated from a specific visit (at which the condition is met) onwards as applicable for the respective group/antigens.
- For codes 1040, 2010, 2040, 2050, 2080: participants will be eliminated from a specific visit (at which the condition is met) onwards.
- 2090, 2100, 2120: participants will be eliminated at the specific visit at which the condition is met.

Table 1 List of elimination codes

Code	Condition under which the code is used	Visit /Contact(timepoints) where the code is checked	Visit from when it is applicable	Applicable for analysis set/endpoint
800	Fraudulent data	All	All	ES and PPS for analysis of immunogenicity
900	Invalid informed consent	All	All	ES and PPS for analysis of immunogenicity
1030	Study intervention not administered at all	All	All	ES and PPS for analysis of immunogenicity
1040	Administration of concomitant vaccine(s) forbidden in the protocol Use of any investigational or non-registered vaccine other than the study interventions during the period beginning 30 days before the first study vaccine administration or planned use during the study period. Planned or actual administration of a vaccine not foreseen by the study protocol in the period starting 30 days	Visit 1,2,3	From the specific visit the condition is met	PPS for analysis of immunogenicity

Code	Condition under which the code is used	Visit /Contact(timepoints) where the code is checked	Visit from when it is applicable	Applicable for analysis set/endpoint
	before the first study intervention administration and ending 30 days after the last study intervention administration. Note: In case an emergency mass vaccination for an unforeseen public health threat (e.g.: a pandemic) is recommended and/or organized by the public health authorities, outside the routine immunization program, the time period described above can be reduced if necessary for that vaccine provided it is used according to the local governmental recommendations and that the Sponsor is notified accordingly.			
1050	Randomisation failure: Subject not randomized in the correct group (To be attributed by Statistician only; Check SBIR, replacement, vaccine administration)	Visit 1	All	PPS for analysis of immunogenicity

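### For a late Visit 2 draw, a licensed non-study vaccine given 31 to 36 days after FLU meets the per-protocol elimination rule in Control but not in Co-Ad; the effect is very small and the rule is cheap to align

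*Protocol*

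**What the plan says.** Protocol 5.2.2 excludes a vaccine not foreseen by the study over a period that opens 30 days ahead of the first dose, "ending 30 days after the last study intervention administration". A note lets that period be shortened for emergency mass vaccination. In SAP 3.1.2, Table 1, code 1040 ("Administration of concomitant vaccine(s) forbidden in the protocol") takes over the same limits, "before the first study intervention administration and ending 30 days after the last study intervention administration", with the same note. The code is checked at Visits 1, 2 and 3, and the SAP says that a participant who meets it will be eliminated from that visit onwards.

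Under Protocol 4.1, Co-Ad receives both vaccines at Visit 1. Control receives FLU at Visit 1, "followed by a single dose of the RSV investigational vaccine at Visit 2 (Day 31").

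SAP section 3 sets the sampling range: "Intervals for the Co-Ad group: Visit1-Visit2=30-37 days". For Control the range is also 30 to 37 days, both from Visit 1 to Visit 2 and from Visit 2 to Visit 3. The HI endpoints are compared at Visit 2 in both groups, on the per-protocol set (PPS).

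Protocol 6.8 requires the eCRF to hold medications and vaccinations "administered during the 30-day period following each dose of study intervention", and also any product that leads to elimination from the analysis.

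Two further passages bear on the Control case. Protocol 7.1.1 says that a Control participant who meets a 5.2.2 criterion should not receive the RSV vaccine at Visit 2. Protocol 9.3.1 says that such a participant *may* be eliminated, where the SAP says *will*.

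**The concern.** The window is anchored to the last study dose, and that dose falls about a month later in Control than in Co-Ad. The HI sample, by contrast, is anchored to the FLU dose, which is at Visit 1 in both groups. Two participants with the same vaccination on the same day before the same sample can therefore be handled differently because of their assigned arm.

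Take a licensed vaccine given 32 days after FLU, with the draw at 36 days. In Co-Ad the window closed at 30 days and code 1040 does not apply. In Control the window is still open and code 1040 applies at Visit 2.

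The PPS carries the confirmatory non-inferiority test, so its membership rule should not depend on arm for the same exposure. The trial is also open-label, and 5.2.2 leaves a Co-Ad participant free to take another vaccine after 30 days while a Control participant is not. Exposure could therefore differ as well as its handling. If a retained vaccine raised HI titers in Co-Ad, the Control/Co-Ad ratio would fall, which favors the non-inferiority claim.

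**Working it through.** **Day counts.** All days are counted from the FLU dose, so the planned Visit 2 (study Day 31) is day 30.

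- Co-Ad: last dose on day 0, so the window closes on day 30.
- Control: last dose at Visit 2, on day 30 to 37, so the window closes on day 30 + 30 = 60 to 37 + 30 = 67.
- Visit 2 draw on day D, with D from 30 to 37 in both groups.

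A whole day before the draw is discordant if it is later than day 30 and earlier than D. The number of such days is max(0, D − 31).

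| Draw on day D | Discordant days before the draw | Count |
|---|---|---|
| 30 | none | 0 |
| 31 | none | 0 |
| 32 | 31 | 1 |
| 33 | 31–32 | 2 |
| 34 | 31–33 | 3 |
| 35 | 31–34 | 4 |
| 36 | 31–35 | 5 |
| 37 | 31–36 | 6 |

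Counting the draw day itself gives 0 to 7. Vaccines on days 0 to 30 are barred in both arms.

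**RSV endpoints.** The RSV dose is the last dose in both arms, and its sample is 30 to 37 days later in both (Visit 2 in Co-Ad, Visit 3 in Control). The window therefore misses the same 0 to 6 days before the draw in each arm.

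**The plan's power, reproduced.** Inputs from Protocol 9.2: 462 per group, SD 0.6 (FLU) and 0.45 (RSV) on log10, true ratio 1.05, margin 1.5, one-sided 2.5%. The distance to the margin is log10(1.5) − log10(1.05) = 0.1761 − 0.0212 = 0.1549. For FLU the standard error is 0.6 × √(2/462) = 0.0395. The noncentral t with 922 degrees of freedom gives 97.50% per FLU strain and 99.95% per RSV endpoint. Summing the type II errors of four strains and two RSV endpoints gives a global power of 89.9%. These match the stated 97.5%, 99.9% and about 90%.

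**Effect of losing Control participants.** The documents give no frequency, so the shares are assumptions. Elimination from Visit 2 onwards also removes the participant from Visit 3, so the loss is applied to all six endpoints.

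| Assumed share of Control lost | Control n | Power per FLU strain | Global power |
|---|---|---|---|
| 0% | 462 | 97.50% | 89.9% |
| 0.5% | 460 | 97.47% | 89.8% |
| 1% | 457 | 97.44% | 89.6% |
| 2% | 453 | 97.38% | 89.4% |
| 5% | 439 | 97.19% | 88.6% |

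These are pessimistic, because 462 is what remains of 514 after the planned 10% non-evaluable share.

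**Effect on the HI GMT ratio.** If a share f of Co-Ad is retained with titers raised k-fold, the mean log10 titer in Co-Ad rises by f × log10(k), and the Control/Co-Ad ratio is multiplied by k^(−f). This ignores covariate adjustment, and both f and k are assumptions.

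- f = 0.5%, k = 1.25: 0.999
- f = 1%, k = 2: 0.993
- f = 5%, k = 4: 0.933

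**The case against.** The best case against acting is that this situation hardly ever arises. It needs a draw at least 2 days after the planned day and another vaccine in the few days between. An unrelated vaccine probably does little to HI titers, and one given 1 to 6 days before the draw has little time to act. All of this stands, and it limits the point to consistency of the rule.

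Elimination in Control is also less certain than the SAP alone suggests. Protocol 9.3.1 leaves it discretionary. Under 7.1.1 the RSV dose should be withheld if 5.2.2 is met; FLU is then the last dose, and the window has arguably closed at 30 days, as in Co-Ad. That makes the rule circular and is itself a reason to reconcile the text.

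The Exposed Set analysis in SAP 4.2 does not apply code 1040 and treats both arms alike. But it runs only if at least 5% of vaccinated participants with serology are excluded in a group, and it complements the confirmatory PPS result without replacing it.

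A reader might infer more than the documents support:

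- *That any vaccination before Visit 2 is handled differently by arm.* Only days 31 to 36 before a late draw are.
- *That the RSV comparison has the same one-sided exclusion.* Its gap is equal in both arms.
- *That another RSV or influenza vaccine could slip through and distort the result.* Protocol 2.2 says that no RSV vaccine is available for older adults, and a separate limb of 5.2.2 and code 1040 bars planned use of investigational or non-registered vaccines throughout the study. All participants have just had the seasonal influenza vaccine in the study, and nothing suggests a second within weeks.
- *That the Co-Ad vaccination would go unseen.* Section 6.8 has staff ask about vaccinations at every visit or contact, and the schedule of activities lists their recording at Visit 2 and Month 6. The text supports only that eCRF entry is not required after 30 days when no elimination follows.

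**Conclusion.** The mismatch is real and follows from the day counts. For a Visit 2 draw 32 to 37 days after FLU, the PPS rule for the primary HI GMT ratio and the secondary seroconversion rate depends on arm, on 1 to 6 days before the draw. No other elimination code covers a routine licensed vaccine in those days. For the RSV endpoints there is only a coverage gap, equal in both arms.

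The size is very small. With 0.5% to 5% of Control lost, power per FLU strain stays above 97%. At an assumed 1% and 2-fold change the ratio is multiplied by 0.993, against a margin of 1.5. Even the extreme assumed case gives 0.933. The frequencies and fold changes are assumptions throughout. Nothing here supports a claim of material bias or inadequate power; this is a low-priority correction to the definition of a confirmatory analysis set.

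**What to change.** In SAP Table 1, define code 1040 separately for each endpoint and let it run through the date of that endpoint's post-dose sample, identically in both arms: Visit 2 for FLU in both groups; Visit 2 in Co-Ad and Visit 3 in Control for RSV. Keep the emergency mass-vaccination allowance. Codes 1070, 1080 and 1090 already work by group and antigen, so the structure exists. The discordant days then fall from at most 6 to 0.

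In Protocol 6.8, extend the required recording of vaccinations to the same sample date.

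Reconcile three passages: the end of the 5.2.2 period with the 30-to-37-day sampling range; 7.1.1 with 5.2.2, because withholding the RSV dose changes which dose is the last; and the *may* of 9.3.1 with the SAP's *will*. Which clinical rule is right is for the sponsor to settle.

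The cost is wording in two documents and one programming rule. Sites already ask about vaccinations at each visit. The downside is that a few Co-Ad participants may leave the PPS. The change should be made before the final analysis, since exclusions settled afterwards in an open-label trial are hard to defend.
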